8.4.2 Method of Detecting AEs, SAEs, and Other Reportable Safety Events

Care will be taken not to introduce bias when detecting AEs and/or SAEs and other reportable safety events. Open-ended and nonleading verbal questioning of the participant is the preferred method to inquire about AE occurrence.

8.4.3 Follow-up of AE, SAE, and Other Reportable Safety Event Information

After the initial AE/SAE report, the investigator is required to proactively follow each participant at subsequent visits/contacts. All AEs, SAEs, and other reportable safety events, including pregnancy and exposure during breastfeeding, ECIs, cancer, and overdose will be followed until resolution, stabilization, until the event is otherwise explained, or the participant is lost to follow-up (as defined in Section 7.3). In addition, the investigator will make every attempt to follow all nonserious AEs that occur in allocated participants for outcome. Further information on follow-up procedures is given in Appendix 3.

8.4.4 Regulatory Reporting Requirements for SAE

Prompt notification (within 24 hours) by the investigator to the Sponsor of SAE is essential so that legal obligations and ethical responsibilities towards the safety of participants and the safety of a study intervention under clinical investigation are met.

The Sponsor has a legal responsibility to notify both the local regulatory authority and other regulatory agencies about the safety of a study intervention under clinical investigation. The Sponsor will comply with country-specific regulatory requirements and global laws and regulations relating to safety reporting to regulatory authorities, IRB/IECs, and investigators.

Investigator safety reports must be prepared for SUSARs according to local regulatory requirements and Sponsor policy and forwarded to investigators as necessary.

An investigator who receives an investigator safety report describing an SAE or other specific safety information (eg, summary or listing of SAE) from the Sponsor will file it along with the IB and will notify the IRB/IEC, if appropriate according to local requirements.

8.4.5 Pregnancy and Exposure During Breastfeeding

Although pregnancy and infant exposure during breastfeeding are not considered AEs, any pregnancy or infant exposure during breastfeeding in a participant (spontaneously reported to the investigator or their designee) that occurs during the study are reportable to the Sponsor.

All reported pregnancies must be followed to the completion/termination of the pregnancy. Pregnancy outcomes of spontaneous abortion, missed abortion, benign hydatidiform mole, blighted ovum, fetal death, intrauterine death, miscarriage, and stillbirth must be reported as serious events (Important Medical Events). If the pregnancy continues to term, the outcome (health of infant) must also be reported.

8.4.6 Disease-related Events and/or Disease-related Outcomes Not Qualifying as AEs or SAEs

Efficacy endpoints as outlined in this section will not be reported to the Sponsor as described in Section 8.4.1.

Specifically, the suspected/actual events covered in this exception include any event that is disease progression of the cancer under study.

The Sponsor will monitor unblinded aggregated efficacy endpoint events and safety data to ensure the safety of the participants in the study. Any suspected endpoint that upon review is not progression of the cancer under study will be forwarded to Global Pharmacovigilance as an SAE within 24 hours of determination that the event is not progression of the cancer under study.

8.4.7 Events of Clinical Interest

Selected serious and nonserious AEs are also known as ECIs and must be reported to the Sponsor.

Events of clinical interest for this study include:

1. An overdose of Sponsor's product, as defined in Section 8.5.
2. All cohorts except HCC-specific expansion cohorts:
An elevated AST or ALT lab value that is greater than or equal to 3X the upper limit of normal and an elevated total bilirubin lab value that is greater than or equal to 2X the upper limit of normal and, at the same time, an alkaline phosphatase lab value that is less than 2X the upper limit of normal, as determined by way of protocol-specified laboratory testing or unscheduled laboratory testing.*

*Note: These criteria are based upon available regulatory guidance documents. The purpose of the criteria is to specify a threshold of abnormal hepatic tests that may require an additional evaluation for an underlying etiology. The study site guidance for assessment and follow up of these criteria can be found in the Investigator Study File Binder (or equivalent).

3. HCC-specific expansion cohort, Arm 2 Part II:
Hepatic ECIs include any of the following events if the events are considered not due to disease progression or TACE as judged by the investigator. All of these events (if not associated with disease progression under study) will require holding study treatment, notification of the event(s) to the Sponsor within 24 hours after awareness via electronic media or paper.

For dose interval modification, refer to Section 6.6.1 (V937) and 6.6.2 (pembrolizumab). For guidance related to the diagnosis and management of hepatic ECIs, refer to Section 6.6.3.

- ALT:
 - Among participants with Baseline ALT $<2 \times$ ULN: ALT $\geq 5 \times$ ULN
 - Among participants with Baseline ALT $\geq 2 \times$ ULN: ALT $>3 \times$ the Baseline level
 - ALT >500 U/L regardless of baseline level

- Total Bilirubin:
 - Total bilirubin >3.0 mg/dL
- Regardless of laboratory values, hepatic decompensation diagnosed clinically, including:
 - New onset clinically detectable ascites requiring intervention for >3 days
 - Hepatic encephalopathy
 - Gastrointestinal bleeding suggestive of portal hypertension (eg, esophageal or gastric varices)

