Diarrhea/Colitis	Grade 2 or 3	Withhold	
 Administer corticosteroids (initial dose of 1 to 2 mg/kg prednisone or equivalent) followed by taper 	
 Monitor participants for signs and symptoms of enterocolitis (ie, diarrhea, abdominal pain, blood or mucus in stool with or without fever) and of bowel perforation (ie, peritoneal signs and ileus) Participants with \geqGrade 2 diarrhea suspecting colitis should consider GI consultation and performing endoscopy to rule out colitis Participants with diarrhea/colitis should be advised to drink liberal quantities of clear fluids. If sufficient oral fluid intake is not feasible, fluid and electrolytes should be substituted via IV infusion
	Recurrent Grade 3 or Grade 4	Permanently discontinue		

irAEs	Toxicity Grade (CTCAE v5.0)	Action With Pembrolizumab Monotherapy, Coformulations or IO Combinations	Corticosteroid and/or Other Therapies	Monitoring and Follow-up
AST or ALT Elevation or Increased Bilirubin	Grade 2 ^a	Withhold	
 Administer corticosteroids (initial dose of 0.5 to 1 mg/kg prednisone or equivalent) followed by taper 	
 Monitor with liver function tests (consider weekly or more frequently until liver enzyme value returned to baseline or is stable)
	Grade 3 ^b or 4 ^c	Permanently discontinue	
 Administer corticosteroids (initial dose of 1 to 2 mg/kg prednisone or equivalent) followed by taper 	
T1DM or Hyperglycemia	New onset T1DM or Grade 3 or 4 hyperglycemia associated with evidence of β -cell failure	Withhold ^d	
 Initiate insulin replacement therapy for participants with T1DM Administer antihyperglycemic in participants with hyperglycemia 	
 Monitor participants for hyperglycemia or other signs and symptoms of diabetes
Hypophysitis	Grade 2	Withhold	
 Administer corticosteroids and initiate hormonal replacements as clinically indicated 	
 Monitor for signs and symptoms of hypophysitis (including hypopituitarism and adrenal insufficiency)
	Grade 3 or 4	Withhold or permanently discontinue ^d		

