6.6.3 Guidance for Management of Hepatic Events of Clinical Interest

HECIs are described in Section 8.4.7. All of these HECIs will require holding study intervention and notification to the Sponsor within 24 hours. All cases of retreatment after interruption of study intervention for HECI must be reported to the Sponsor and recorded in the database. As per Section 8.4.7, HECIs are not the result of disease progression or ITu liver lesion injection complications; and therefore, the following evaluations are not required for these etiologies.

Immediate assessment in case of HECI:

All Participants

- All participants should be considered for evaluation according to the directions below within 72 hours of the alert for a non-overdose ECI.

- Procedures:
 - Consider obtaining a consultation with a hepatologist
 - Obtain a work-up for hepatitis if there is no underlying hepatitis, including hepatitis A, B, C, D, E, Epstein-Barr virus, and cytomegalovirus
 - Assess for ingestion of drugs/supplements with hepatotoxic potential
 - Assess for alcohol ingestion
 - Assess for potential bacterial infection, biliary obstruction, or occult gastrointestinal bleeding
 - Repeat ALT, AST, Tbil, Dbil, ALP, INR, and CBC with differential; GGT testing must be performed as part of the HECI workup
 - Measure HCV RNA viral load (applies only for participants who have current active HCV infection or had infection in the past)
 - HBV DNA, HBsAg, HBeAg, anti-HBc (total and IgM), anti-HBe, and anti-HBs regardless of prior HBV status (Note: participants should be questioned about compliance with the use of antiviral agents)
 - Other laboratories or imaging studies as clinically indicated
 - Consider liver biopsy if indicated

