Relapse of HCV infection for participants with successfully treated or new HCV infection	If HCV RNA was TND at baseline, and now has confirmed detectable HCV RNA (2 specimens, 1 week apart)	
Interrupt intervention for up to 12 weeks. Assess use of injection or inhalation drugs. Recheck HCV genotype at the time of relapse of HCV RNA to rule out new infection. Measure safety labs for AST, ALT, ALP, Tbil, Dbil, and INR on weekly basis. Measure HCV RNA levels every 2 weeks. Please discuss risk benefit with Sponsor prior to starting HCV antiviral therapy. Restart intervention only if ALT returns to normal or Grade 1 (if normal at baseline), or to baseline grade (if Grade 2 at baseline) within 12 weeks, and the participant is clinically stable; otherwise, the participant should be permanently discontinued.

Event	Diagnosis	Management
Immune-related Hepatitis	
If any of the HECI criteria are met as defined in the protocol Section 8.4.7
 
Note:
 
Immune-related hepatitis is a diagnosis made after excluding other possible etiologies such as viral flare, biliary or vascular obstruction, infection, medications, and alcohol use usually immune-related hepatitis response to dechallenge and/or steroids and reoccurs with rechallenge.
	
Interrupt intervention for up to 12 weeks. Start IV corticosteroid 60 mg/day of prednisone or equivalent followed by oral corticosteroid. Monitor with biweekly laboratory tests, including AST, ALT, Tbil, Dbil, ALP, and INR.
 
Restart intervention only if:
 
 Abnormal laboratory values resolve to Grade ≤ 1 or baseline (if abnormal at baseline) Taper steroid over 28 days Steroid treatment is tapered to prednisone < 10 mg/day or equivalent 
Permanently Discontinue intervention if:
 
 Laboratory abnormalities do not resolve within 3 weeks Steroids cannot be lowered to ≤ 10 mg/day (or prednisone equivalent) within 12 weeks Decompensation to CP-C status

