- Any study intervention-related toxicity specified as a reason for permanent discontinuation as defined in the guidelines for dose modification due to AEs in Section 6.6.
- Completion of 35 treatments with pembrolizumab.

Note: 35 cycles (approximately 2 years) are calculated from the first dose.

- Side effects and/or concomitant medications required for treatment of HIV and/or its complications that are incompatible with continued study treatment (exceptions are permissible, but should be discussed with the Sponsor)
- Participant has any of the following non-overdose HECIs:
 - ALT $>20 \times$ ULN
 - Child-Pugh score of ≥ 9 points
 - Gastrointestinal bleeding suggestive of portal hypertension (eg, esophageal or gastric varices)
 - New onset of clinically detectable ascites
 - Hepatic encephalopathy

- Recurrence of a severe or life-threatening event, or of any of the laboratory abnormalities listed above, that are presumed to be immune-related

For participants who are discontinued from study intervention, but continue to be monitored in the study, all visits and procedures, as outlined in the SoA, should be completed.

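### For Cohort D, Sections 8.4.7 and 6.6.3 exclude different causes from hepatic events of clinical interest, and Tables 14 and 16 give opposite instructions for an immune-related Grade 3 ALT rise

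*Combined protocol and SAP*

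**What the plan says.** Section 8.4.7 defines the HCC-specific hepatic events by laboratory thresholds and clinical decompensation, "if the events are considered not due to disease progression or TACE as judged by the investigator". On action it states: "All of these events (if not associated with disease progression under study) will require holding study treatment", with notification to the Sponsor within 24 hours.

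Section 6.6.3 sets out the work-up and describes the definition differently: "As per Section 8.4.7, HECIs are not the result of disease progression or ITu liver lesion injection complications". It then waives the work-up for those causes.

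Three places deal with stopping:

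- **Table 14 (6.6.2)**, row "AST or ALT Elevation or Increased Bilirubin": Grade 2 is withheld; Grade 3 or 4 is a permanent stop. There is no HCC exception.
- **Table 16 (6.6.3.1)**, immune-related hepatitis row, which applies once any 8.4.7 criterion is met: a pause of at most 12 weeks, with restart conditional on laboratory recovery and steroid taper. Permanent stops are non-resolution within 3 weeks, failure to lower steroids within 12 weeks, and "Decompensation to CP-C status".
- **Section 7.1**, under "Participant has any of the following non-overdose HECIs": ALT above 20 x ULN, a Child-Pugh score of 9 or more, portal-hypertensive bleeding, new ascites or encephalopathy. The same list also takes in every permanent stop specified in Section 6.6.

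Sections 3 and 9.1 name discontinuation of study intervention due to an AE as a primary endpoint for Arm 2, which includes Cohort D.

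**The concern.** In Cohort D the liver injection is the experimental procedure, so whether the injection caused a hepatic event is the main attribution question. HCC was excluded from dose escalation (5.1.3), so Cohort D is this trial's first hepatic safety evidence in HCC, and the synopsis lists no Data Monitoring Committee. The 24-hour HECI report is therefore one of the main routes by which the Sponsor hears of such events quickly.

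Two sites following the text in good faith could treat the same patient differently. One holds treatment, reports within a day and works the event up; the other does none of these under the HECI rules. For an immune-related Grade 3 rise, one records a permanent discontinuation and the other an interruption. The second difference feeds a primary endpoint.

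**Working it through.** The check is mainly textual. The plan states no figure on this point that could be reproduced.

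**1. Attribution.** Take an ALT of at least 5 x ULN from a baseline below 2 x ULN, judged to be caused by the V937 injection.

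| | 8.4.7 | 6.6.3 |
|---|---|---|
| Named exclusions | progression, TACE | progression, injection complications |
| Is it a HECI? | yes | no |
| Consequence | hold, 24-hour report | work-up not required |

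TACE is not among the interventions in Table 9, is mentioned nowhere else in the document and is missing from the abbreviation list. The cross-reference in 6.6.3 therefore attributes to 8.4.7 something it does not say.

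**2. Table 14 against Table 16.** Inputs: Table 14 footnote b (Grade 3 is above 5 and up to 20 times ULN from a normal baseline, or the same multiples of an abnormal baseline); 8.4.7 (ALT at least 5 x ULN if baseline is below 2 x ULN, otherwise above 3 x baseline).

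For ALT of 8 x ULN from a normal baseline, 5 < 8 ≤ 20, so it is Grade 3 and Table 14 requires a permanent stop. Also 8 ≥ 5, so a HECI criterion is met and, if the event is immune-related, Table 16 interrupts with restart possible. Values of 5.5, 15 and 20 x ULN give the same pair. At 21 x ULN, Table 14 and the ALT line in 7.1 both stop; Table 16 still begins with an interruption.

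The affected range depends on baseline, and Table 8 admits ALT up to 5 x ULN:

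| Baseline ALT (x ULN) | HECI threshold (x ULN) | Table 14 Grade 3 above (x ULN) | 7.1 ALT line above (x ULN) |
|---|---|---|---|
| 1 (normal) | 5 | 5 | 20 |
| 2 | 3 × 2 = 6 | 5 × 2 = 10 | 20 |
| 3 | 3 × 3 = 9 | 5 × 3 = 15 | 20 |
| 5 | 3 × 5 = 15 | 5 × 5 = 25 | 20 |

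A range of 5 to 20 x ULN for Grade 3 therefore holds only for a normal baseline. At a baseline of 5 x ULN, the 7.1 line is reached before Grade 3.

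**3. Secondary wording.**

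- Encephalopathy and portal-hypertensive bleeding: 8.4.7 asks for a hold; 7.1 for discontinuation.
- Ascites: 8.4.7 counts it only if intervention is needed for more than 3 days. 7.1 lists it as a HECI without that condition.
- Child-Pugh: 7.1 stops at 9 or more. Appendix 9 puts 9 in class B (7–9) and starts class C at 10, so the Table 16 line is not met at 9; both are met at 10.

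**4. Size.** With 30 planned HCC participants, one reclassified participant moves a rate by 1/30 = 3.3 points (exact 95% CI for 1/30: 0.1% to 17.2%). The same interval method gives 2.1% to 26.5% for 3/30, matching Table 20.

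Section 6.6.3.1 puts immune-related hepatitis on pembrolizumab at about 1%. At that rate, 30 × 0.01 = 0.3 cases are expected, and the chance of at least one is 1 − 0.99^30 = 26%. The rate is not stated for this combination. If it were 5% (my assumption), 30 × 0.05 = 1.5 cases would be expected, with a 1 − 0.95^30 = 79% chance of at least one.

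**The case against.** Much of the apparent conflict dissolves on a careful reading, and two stronger inferences should be resisted.

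A reader might infer that Section 7.1 sets a third, incompatible ALT threshold by discontinuing only above 20 x ULN. It does not. Its list is additive and brings in every permanent stop from Section 6.6, so an ALT of 8 x ULN does not escape it. Likewise, Child-Pugh 9 and class C can both be obeyed: 7.1 is mandatory, and Table 16 does not say that class C is the only trigger. These lines need alignment, but they are not direct contradictions.

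A reader might also infer that Cohort D liver events cannot be counted consistently. Section 8.4.1 requires all AEs to be reported from allocation to 30 days after treatment ends, whether or not they are ECIs, and Section 9.6.2 summarises AEs by dose level and/or cohort. HECI is not among the endpoints named in 9.4.2. Total AE counts are safe.

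It can further be said that the documents divide the work: 8.4.7 and 6.6.3.1 send dose-interval changes to 6.6.1 and 6.6.2, and diagnosis and management to 6.6.3 and Table 16. This helps only in part, because Table 16 contains its own interrupt, restart and permanent-stop rules. Nor does the import clause in 7.1 settle the matter, since both tables sit in Section 6.6 and nothing ranks them.

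Finally, the events may be few and the study is winding down. That bears on priority; the text still conflicts.

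**Conclusion.** Two internal contradictions stand. Sections 8.4.7 and 6.6.3 disagree on whether an injection-caused hepatic event is a HECI, and Tables 14 and 16 disagree on an immune-related Grade 3 ALT rise, with no stated precedence. The hold-versus-discontinue, ascites and Child-Pugh differences are secondary mismatches.

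What is affected is the HECI flag, the hold, the 24-hour report, the work-up and the Arm 2 primary endpoint of discontinuation due to an AE. Each affected participant is worth 3.3 points at the planned 30, and more if the cohort is smaller. How many would be affected is unknown: about 0.3 immune-related cases at the documents' 1% rate, 1.5 at an assumed 5%. No rate is given for injection-caused events.

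This is an inconsistency that should be fixed; it does not undermine the safety analysis. The study is being discontinued, Cohort D may fall short of 30, and the number treated is not stated. If none were treated, the effect is on the written record only.

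**What to change.** 1. Reconcile 8.4.7 with 6.6.3 on whether hepatic events caused by the V937 injection are HECIs, correct the cross-reference, and remove or explain TACE.
2. Reconcile Tables 14 and 16 with Section 7.1 and state which governs hepatic interruption and discontinuation in Cohort D. Align the hold/discontinue, ascites and Child-Pugh wording at the same time. The choice of clinical rule is for the sponsor; this review takes no position on it.
3. In the safety output, tabulate all Cohort D events meeting the 8.4.7 laboratory thresholds, whatever their attributed cause, with attribution as a column. The count then does not depend on which exclusion a site applied.

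The cost is protocol wording plus one extra table from laboratory data already collected. This amendment already edits the HECI guidance in 6.6.3 (the GGT addition), so the section was open for change. If Cohort D participants have been treated, item 3 is worth doing even if the wording is not amended again.

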8.5 Treatment of Overdose

For purposes of this study, an overdose will be defined as any dose exceeding the prescribed dose for V937 by $>50\%$ of the indicated dose or a pembrolizumab dose of ≥ 1000 mg (≥ 5 times the indicated dose). No specific information is available on the treatment of overdose of V937 or pembrolizumab. In the event of overdose, V937 or pembrolizumab should be discontinued and the participant should be observed closely for signs of toxicity. Appropriate supportive treatment should be provided if clinically indicated.

8.6 Pharmacokinetics

PK supports evaluation of V937 immunogenicity and exposure in this indication, and evaluation of exposure of the proposed dosing regimen. Blood samples will be obtained to evaluate V937 exposures which are used to derive PK parameters (AUC and C_{max}) and immunogenicity.

If ongoing PK and neutralizing antibody analysis is deemed to be unnecessary by the Sponsor, it may be reduced or discontinued.

PK sample collection is no longer required.

8.6.1 Blood Collection for Serum V937

PK sample collection is no longer required.

8.6.2 Blood Collection for Neutralizing V937 Antibodies

Neutralizing V937 antibodies sample collection is no longer required.

8.7 Pharmacodynamics

Pharmacodynamic sample collection is no longer required.

8.8 Biomarkers

To identify novel biomarkers, the following biospecimens to support exploratory analyses of cellular components (eg, protein, RNA, DNA, metabolites) and other circulating molecules will be collected from all participants in this study as specified in the SoA (collection no longer required):

- Blood for genetic analysis
- Blood for RNA analyses
- Blood for ctDNA analyses
- Tumor biopsy

8.8.1 Planned Genetic Analysis Sample Collection

The planned genetic analysis sample should be drawn for planned analysis of the association between genetic variants in DNA and drug response. This sample will not be collected at the site if there is either a local law or regulation prohibiting collection, or if the IRB/IEC does not approve the collection of the sample for these purposes. If the sample is collected, leftover extracted DNA will be stored for future biomedical research if the participant provides documented informed consent for future biomedical research. If the planned genetic analysis is not approved, but future biomedical research is approved and consent is given, this sample will be collected for the purpose of future biomedical research.

